# 4.0 BACKGROUND

# 4.1 Disease Background

Prostate cancer (PC) is the most commonly diagnosed malignancy and the second leading cause of cancer death in men. Radical prostatectomy and radiation therapy are the established definitive treatments for clinically localized PC; yet, 50,000 men each year progress with a biochemical relapse while others develop metastatic disease resulting in over 30,000 deaths annually. While chemical castration is temporarily effective in many patients, most men eventually progress to castrate-resistant prostate cancer (CRPC) and are then treated with docetaxel-based chemotherapy.

[figure not shown]

Figure 1: Clinical states of prostate cancer

# 4.2 Treatment Background

#### 4.2.1 Description and mechanism of action of Olaparib

PARP functions in the DNA repair pathway, specifically by serving in base excision repair of DNA single strand breaks. Inhibition of PARP results in inability for cells to repair single strand breaks. Cells normally would employ the error-free homologous recombination pathway to repair such defects. However, in tumors that harbor defects in these DNA repair genes (such as BRCA1/2), the strand breaks lead to chromosomal instability and eventually cell death. Olaparib functions in cells to inhibit various isoforms of PARP.

Investigators should be familiar with the current olaparib (AZD2281) Investigator Brochure (IB).

[figure not shown]
Olaparib (AZD2281, KU-0059436) is a potent polyadenosine 5'diphosphoribose [poly (ADP ribose)] polymerization (PARP) inhibitor (PARP-1, -2 and -3) that is being developed as an oral therapy, both as a monotherapy (including maintenance) and for combination with chemotherapy and other anti-cancer agents. Olaparib [Lynparza] was approved by the FDA for treatment of men with prostate cancer who have deleterious or suspected deleterious germline or somatic homologous recombination repair gene-mutated metastatic castration resistant prostate cancer who have progressed on Abiraterone or Enzalutamide.

PARP inhibition is a novel approach to targeting tumors with deficiencies in DNA repair mechanisms. PARP enzymes are essential for repairing DNA single strand breaks (SSBs). Inhibiting PARPs leads to the persistence of SSBs, which are then converted to the more serious DNA double strand breaks (DSBs) during the process of DNA replication. During the process of cell division, DSBs can be efficiently repaired in normal cells by homologous recombination repair (HR). Tumors with HR deficiencies (HRD), such as ovarian cancers in patients with BRCA1/2 mutations, cannot accurately repair the DNA damage, which may become lethal to cells as it accumulates. In such tumor types, Olaparib may offer a potentially efficacious and less toxic cancer treatment compared with currently available chemotherapy regimens.

BRCA1 and BRCA2 defective tumors are intrinsically sensitive to PARP inhibitors, both in tumor models and in the clinic. The mechanism of action for olaparib results from the trapping of inactive PARP onto the single-strand breaks preventing their repair. Persistence of SSBs during DNA replication results in their conversion into the more serious DSBs that would normally be repaired by HR repair. Olaparib has been shown to inhibit selected tumor cell lines in vitro and in xenograft and primary explant models as well as in genetic BRCA knock-out models, either as stand-alone treatment or in combination with established chemotherapies.

#### 4.2.2 Description and mechanism of action of Ascorbic Acid

The mechanism of action of ascorbic acid-mediated tumor suppression appears to depend on hydrogen peroxide production in extracellular fluid; hydrogen peroxide induces necrosis in tumor cells but not in normal cells. Ascorbic acid treatment inhibits prostate cancer cell growth through three mechanisms: (1) ascorbic acid induces  $H_2O_2$ -dependent cytotoxicity in prostate cancer cells, (2) ascorbic acid treatment decreased ATP levels in prostate cancer cells, and (3) ascorbic acid treatment induced autophagy in prostate cancer cells. Ascorbic acid treatment also suppresses metastases in hormone-refractory prostate cancer. Cytotoxicity of ascorbic acid requires mM concentrations. The dose response curve for ascorbic acid on DU-15 and PC-3 prostate cancer cells, shown below (Source: Levine, NCI Developmental Therapeutics Program NSC 33832), demonstrate that ascorbic acid was more effective for DU 145, with nearly complete kill at 10 mM and produced no growth for PC3.

**Figure 2:** Dose response curve for ascorbic acid in DU-15 and PC-3 prostate cancer cells (Source: Levine, NCI Developmental Therapeutics Program NSC 33832)

Bioavailability of ascorbic acid is tightly controlled in response to oral administration and reaches only 100  $\mu$ M with consumption of five servings of fruits and vegetables, which contain approximately 250 mg of ascorbic acid. Oral supplementation even at many grams does not increase plasma concentration beyond 250  $\mu$ M. IV administration bypasses the tight controls found with oral administration, and produces pharmacological ascorbic acid concentrations of 25-30 mM. Pharmacological ascorbic acid concentrations of 10mM can be maintained for approximately 4 hours with infusion rates of 0.5 – 1.0 g/kg per minute.

#### 4.2.3 Preclinical studies of Olaparib

The pre-clinical experience is fully described in the current version of the olaparib Investigator's Brochure (IB).

Olaparib has demonstrated in vitro and in vivo efficacy in preclinical studies in certain prostate cancer cell lines. The study of Brenner et. al. tested VCaP cells in vitro and as xenografts and demonstrated efficacy of olaparib monotherapy compared to controls. Efficacy in 22Rv1 cell line xenografts was similarly seen with olaparib in a separate study. These included PC3 cells and LNCaP cells.

[figure not shown]
# 4.2.4 Preclinical studies of Ascorbic acid

*Gulo-/-* murine models are deficient in the enzyme responsible for in vivo ascorbic acid synthesis, mimicking human's need for an exogenous source of ascorbic acid. In a hepatoma xenograft *Gulo-/-* mouse model, ascorbic acid given orally did not inhibit tumor growth. However, parenteral ascorbic acid was successful in inhibiting tumor

[figure not shown]
growth in these mice. This preclinical evidence provides support for intravenous infusion of ascorbate.

Linus Pauling first considered ascorbic acid as a treatment for cancer in the early 1970s. However, this research stalled for several years after investigators at the Mayo Clinic found cancer treatment with oral ascorbate to be ineffective. Recent insight into the pharmacokinetic properties of ascorbate revealed that ascorbate must be administered intravenously in order to achieve plasma concentrations necessary to effectively kill cancer cells. With a renewed focus on intravenous dosing, ascorbate has proved to be lethal to and highly selective for a variety of cancer cell types. There are several mechanisms currently under investigation to explain how ascorbate exerts anti-cancer effect; however, a simplified model depicts ascorbate as a pro-drug for reactive oxygen species (ROS), which accumulate intracellularly and generate DNA damage. The complete pre-clinical experience is described in the current version of the Ascorbic Acid Investigator's Brochure (IB).

**4.2.5 Preclinical evidence to support combination Olaparib and Ascorbate** Combination IV ascorbate and PARP inhibitors shows synergy of antitumor activity in two CRPC xenograft models, C4-2 and 22Rv-1. These results are shown in figures 2 and 3.

[figure not shown]

**Figure 3.** Ascorbate enhances the killing of C4-2 and 22Rv1 cells by PARP inhibitors. A) C4-2 cells were seeded in IMEM and allowed to settle overnight. They were then treated with a range of doses for three different PARP inhibitors: olaparib (left), niraparib (middle), and talazoparib (right) either alone or in combination with a sub-lethal dose of ascorbate (1mM). B) 22Rv1 cells were seeded in DMEM and allowed to settle overnight. They were then treated with a range of doses for the same three PARP inhibitors either alone or with a sub-lethal dose of ascorbate  $(50\mu\text{M}).^{20}$ 

[figure not shown]

**Figure 4. CompuSyn was used to generate a combination index.** >1 denotes antagonism, =1 denotes an additive effect, <1 denotes synergism^20

An *in vivo* model (figure 4) demonstrated that the combination of olaparib and ascorbate significantly slowed tumor growth compared to vehicle controls and monotherapy (results shown in figure 5). 

**Figure 5:** *In vivo* model of C4-2 cells, transplanted into mice and exposed to 4g/kg ascorbate daily, 50 mg/kg olaparib daily, a combination of the two agents daily, or a control

**Figure 6:** *In vivo* efficacy was profound in a model using castrated mice to mimic the effect of hormone therapy. While there was some antitumor effect with the single agents, there was a significant delay in tumor doubling time when the agents were used in combination.

# 4.2.6 Clinical Efficacy and Safety of Olaparib

Many trials have studied the clinical efficacy and safety of olaparib. The complete clinical experience with olaparib, including toxicology and safety pharmacology, is fully described in the current version of the olaparib Investigator's Brochure.

Small numbers of advanced prostate cancer patients were included in initial clinical studies of olaparib. In the initial phase I report on olaparib, 3 patients with prostate cancer were included. In a follow-up study of patients with germline BRCA mutations, 8 prostate cancer patients were included.

Recently, a larger cohort of prostate cancer patients treated with olaparib was published. Patients were treated with the FDA-approved dose of 400mg by mouth twice daily. In the trial, 50 patients were enrolled. Three patients discontinued olaparib due to adverse events. There were 30 adverse events of grade 3-4 level. Grade 3-4 events occurring in greater than 1 patient were anemia (20%), fatigue (12%), leukopenia (6%), neutropenia and thrombocytopenia (4%).

Of the patients in the study, 16 were identified to have a mutation in DNA repair genes (BRCA1, BRCA2, ATM, FANCA, CHEK2, PALB2, HDAC2, RAD51, MLH3, ERCC3, MRE11, or NBN). Eleven of 49 evaluable patients experienced a greater than 50% decline in PSA (a PSA $_{50}$  response). Six patients achieved a partial radiographic response by RECIST criteria. Every patient with a radiographic response also had a PSA $_{50}$  response. Of these 11 responders in the study, 10 were among the patients with the mutations in the tested DNA repair genes. One responder was among the remaining 33 without an identified mutation.

There are currently no studies published in hormone sensitive prostate cancer patients.

#### **Clinical Studies in All Diseases**

The largest pool of data for olaparib is drawn from a phase II trial of patients with germline deleterious BRCA 1 or 2 mutations. That study included 298 patients, including 193 with ovarian cancer and 62 with breast cancer. The analysis of the ovarian cancer cohort in this study led to the FDA-approved Olaparib. The overall tumor response rate by RECIST criteria was 26.2% across all tumor types. Specifically for the ovarian cancer cohort, the median response duration was 7.9 months.

Adverse events were reported in the trial and are summarized in Table 1 below:

**Table 1.** Events occurring in >15% (any grade) or >5% (grade 3-4) in the trial.

Adverse Event	Any Grade Toxicity	Grade 3-4 Toxicity
Fatigue	59.1%	6.4
Nausea	59.1%	0.3
Vomiting	37.2%	2.3
Anemia	32.9%	17.4
Diarrhea	27.2%	1.3
Abdominal Pain	25.8%	5.7
Decreased Appetite	20.8%	0.3
Dyspepsia	17.4%	0.0
Headache	16.1%	0.3
Dysgeusia	15.8%	0.0

# 4.2.7 Clinical Efficacy and Safety of IV Ascorbic Acid

Multiple phase I trials of IV ascorbic acid safety and phase I/II trials of IV ascorbic acid safety and efficacy in cancer patients have been published. In one trial ascorbic acid in elderly patients with advanced cancer who had failed all other therapies, 2 patients had unexpectedly stable disease after 8 weeks of ascorbic acid treatment. In a trial of patients with metastatic stage 4 pancreatic cancer who received primary therapy with ascorbic acid, gemcitabine, and erlotinib, 8 of 9 patients had tumor shrinkage after 8 weeks of therapy as measured by CT imaging. A phase I trial of patients with metastatic stage 4 pancreatic cancer who were treated with gemcitabine + IV ascorbic acid as primary therapy until tumor progression showed few toxicities associated with the treatment. The 9 patients had a tripling of disease free internal in comparison to literature controls, and doubling of survival compared to retrospective controls. In a dose escalation study, no toxicity was found at doses even above 1.5g/kg, the doses used in the other three trials. In addition, a phase I/II trial of high-dose, IV ascorbic acid reduced grade 1 and 2 toxicities associated with carboplatin and paclitaxel treatment by more than 50% in women with ovarian cancer in a small, randomized clinical trial. Patients receiving IV ascorbic acid reported lower levels of low-grade gastrointestinal, hepatobiliary, dermatological, immune/infection, pulmonary and renal toxicities commonly associated with carboplatin and paclitaxel treatment. A trial enrolling women with breast cancer randomized to IV ascorbic acid or placebo, in the first year following surgery, showed significant reductions in nausea (p=0.022), loss of appetite (p=0.005), fatigue (p=0.023), dizziness (p=0.004) and hemorrhagic diathesis (p=0.032). Reduced toxicities were experienced by patients independent of whether they were being treated with chemotherapy. Similarly, a phase I/II study of arsenic trioxide/bortezomib/ascorbic acid combination therapy for the treatment of relapsed or refractory multiple myeloma with ascorbic acid IV on days 1, 4, 8, and 11 demonstrated a response rate of 27% in a heavily pretreated population. Ascorbic acid demonstrates activity at twice a week dosing. Taken together, these data support the starting dose of 1g/kg of ascorbic acid in patients with CRPC and mCRPC.

Intravenous ascorbic acid is in wide use by practitioners of complementary and alternative medicine. Estimates are that in the US approximately 10,000 patients receive IV ascorbic acid each year at average doses of 0.5/kg, with average number of doses of twenty per patients. Using multiple tracking mechanisms, minimal adverse events were reported in properly screened patients.

**4.2.8 Clinical efficacy and safety of combination Olaparib and IV Ascorbate** This trial seeks to assess the combination of olaparib and IV ascorbic acid in men with castration resistant prostate cancer. There is no clinical data to support this combination at this time as these two agents have not been combined in the past to treat castration resistant prostate cancer. The CRPC patient population is in desperate need of new treatment options, and the *in vitro* and *in vivo* data suggest that the combination of olaparib and ascorbate may be effective. The proposed clinical trial aims to determine the safety, tolerability, and provide preliminary data on efficacy of combining olaparib with intravenous ascorbate for the treatment of advanced prostate cancer.

A drug-drug interaction between ascorbic acid and olaparib is not anticipated based on drug metabolism and drug transporters. Olaparib metabolism is primarily mediated by CYP3A4/5. Clinical drug-drug interactions have been noted with strong or moderate CYP3A4 inhibitors or a moderate CYP3A4 inducer. Olaparib is a substrate for Pgp. Olaparib is an inhibitor of CYP3A4, UGT1A1, Pgp, OATP1B1, OCT1, OCT2, OAT3, MATE1, and MATE2K in vitro. Olaparib is an inducer of CYP1A2, CYP2B6 (potentially clinically relevant), CYP3A4, and P-gp. Ascorbic Acid is reversibly oxidized to dehydroascorbic acid (DHA) and metabolized to inactive compounds including ascorbic acid-2-sulfate and oxalic acid. No drug interactions have been noted via the CYP450 pathway. Ascorbic acid is a substrate of two sodium-ascorbate co-transporters (SVCT; both members of the SLC23 family). Oxalic acid is a substrate of OAT3 and inhibitor of OATP1B1. There is a potential for an interaction via the drug transporters at the oxalic acid level but would not be anticipated to be clinically relevant. Therefore, a formal pharmacokinetic assessment will not be conducted.

# 4.3 Rationale for combination Olaparib and Ascorbic Acid

There is significant evidence supporting single agent tumor stability of olaparib in DNA repair mutant prostate cancer and of the effectiveness of ascorbate in reducing toxicities of chemotherapy. The ability to manipulate DNA damage repair has made PARPi an attractive option for combination with DNA damaging agents, such as ascorbate. We therefore hypothesize that ascorbate's ability to generate damage-inducing ROS would benefit from the addition of a PARP inhibitor designed to impede a tumor cell's ability to repair DNA damage. Historically, response to olaparib was 88% in HRD+ and 6% in HRD- mCRPC patients. Per the data described in **Section 4.2**, as well as data from Ma et al, we hypothesize that the combination of olaparib and ascorbic acid will synergize and increase efficacy to be greater than 6% with acceptable toxicities.

#### 5.0 PATIENT SELECTION

# 5.1 Inclusion Criteria

Patients are eligible to be included in the study only if they meet *all* of the following criteria:

- [1] Have metastatic castration-resistant prostate cancer (prostate cancer progressing by PSA (rise by 25% on prior therapy) or imaging despite castrate levels of testosterone [<50 ng/dL] using standard measures of progression defined by Prostate Cancer Working Group).
- [2] Have a minimum PSA of 1 ng/mL.
- [3] Have a pathological diagnosis of prostate carcinoma.
- [4] Have been receiving and will continue to receive continuous hormonal ablation with surgical or medical castration with baseline testosterone <50ng/dL.
- [5] May be receiving bone-targeted agents.
- [6] May have received multiple lines of therapy including radium 223, sipuleucel T, and up to 2 lines of chemotherapy (One of 2 lines may be for hormone sensitive metastatic prostate cancer or both can be for castration resistant).
- [7] Age  $\geq$  18.
- [8] Have ECOG performance status 0-1 (Appendix A).
- [9] Be able to take oral medication and willing to consider a port for ease of administration of ascorbate.
- [10] Must have progressed on one systemic line of treatment (can include LHRH agonist/antagonist or orchiectomy and at least one additional line of therapy (abiraterone, enzalutamide, apalutamide, darolutamide, docetaxel, etc)).
- [11] Have normal organ and marrow function measured within 28 days prior to administration of study treatment as defined below:

- Absolute neutrophil count  $>1.5 \times 10^9/L$ -Platelets  $> 100,000/mm^3$ 

-Hemoglobin > 9g/dL with no blood transfusion in the

past 28 days

-Total bilirubin < 1.5 x ULN

-AST (SGOT)/ALT(SGPT)  $\leq$  2.5 x ULN (<5x ULN if with known liver

metastases provided bilirubin is normal

-Creatinine  $\leq$  1.6 x ULN (for patients with  $\geq$  1.6 x ULN, calculated

or measured creatinine clearance must be > 60

mL/minute (Cockcroft-Gault).

- [12] Men of reproductive potential and those who are surgically sterilized (i.e. post-vasectomy) must agree to practice effective barrier contraception that has an expected failure rate of <1% during and for 6 months after discontinuation of study treatment. Female partners should also use a highly effective form of contraception ([see **Appendix C** for acceptable methods]) if they are of childbearing potential.
  - o If condoms are used as a barrier contraceptive, a spermicidal agent should be added to ensure that pregnancy does not occur.
- [13] Have the ability to understand and have given written informed consent before performance of any study-related procedures not part of normal medical care, with the understanding that consent may be withdrawn by the subject at any time without prejudice to future medical care.

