#### 7.2 Screening/Pretreatment Assessment (up to Day -28)

Before initiating any screening activities, the scope of the study should be explained to each patient. Patients should be advised of any known risks inherent to the planned procedures, any alternative treatment options, their right to withdraw from the study at any time for any reason, and their right to privacy. After this explanation, patients should be asked to sign and date a Notice of Privacy Practice research authorization/HIPAA form and an IRB-approved statement of informed consent that meets the requirements of the Code of Federal Regulations (Federal Register Vol. 46, No. 17, January 27, 1981, part 50).

The following assessments will be performed at the screening visit:

- Obtain informed consent and research authorization.
- Record demographics (including age) and medical history (including prior treatment for prostate carcinoma).
- Conduct physical exam (including vital signs, height/weight).
- Obtain history regarding prior treatment history for prostate cancer (including history of ADT, and history of radiation therapy or other local therapy).
- Obtain histologic/radiographic confirmation of disease. If radiographic studies have not been performed within 6 weeks prior to Cycle 1 Day 1, they must be obtained as part of screening.
- Perform laboratory tests: complete blood count w/diff, PSA, comprehensive metabolic panel, urinalysis, G6PD, testosterone.
- Baseline ECG
- Confirmation of 25% PSA rise on prior therapy.
- Determine suitability for olaparib and ascorbate therapy.
- Discuss concurrent medications.

Relevant information should be documented for registration and monitoring purposes. The institutional registration should be finalized, and appropriate documents faxed or emailed to the lead site/sponsor per **Section 6.0**.

Information for patients who do not meet the eligibility criteria to participate in this study (i.e. screening failures) should be captured in consortium database at the pretreatment assessment.

For any subject that has a DNA repair gene mutation identified during screening and is therefore not eligible for this trial will be referred to medical genetics for counseling and consideration of further targeted testing to determine if the identified mutation is present in the germline.

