# 7.3.1 Clinical, Laboratory, and Radiographic Assessments

Every week, patients will have a non-fasting blood drawn for the values listed below. Repeat labs are not needed on C1D1 as long as visit is within 7 days of screening visit blood draw.

CMP

**Note:** Patients with creatinine clearance between 51-100 mL/min either at trial enrolment or during the course of the trial should be monitored every week for laboratory assessment and toxicity evaluation.

On Day 1 of each cycle, patients will have a non-fasting blood drawn for the values listed below. Repeat labs are not needed on C1D1 as long as visit is within 7 days of screening visit blood draw.

- CBC
- PSA

Every 3 cycles, patients will have radiographic studies:

- CT chest, abdomen, and pelvis with contrast
- NM bone scan

Laboratory Safety Assessments

Full hematology assessments for safety (hemoglobin, red blood cells [RBC], platelets, mean cell volume [MCV], mean cell hemoglobin concentration [MCHC], mean cell hemoglobin [MCH], white blood cells [WBC], absolute differential white cell count (neutrophils, lymphocytes, monocytes, eosinophils and basophils) and absolute neutrophil count or segmented neutrophil count and Band forms should be performed at each Day 1 visit and when clinically indicated. If absolute differentials not available, please provide % differentials. Coagulation [activated partial thromboplastin time (APTT) and international normalized ratio (INR)] will be performed at baseline and if clinically indicated. Patients taking warfarin may not participate in this study.

Biochemistry assessments for safety (sodium, potassium, calcium, glucose, creatinine, total bilirubin, gamma glutamyl transferase [GGT], alkaline phosphatase [ALP], aspartate transaminase [AST], alanine transaminase [ALT], urea or blood urea nitrogen [BUN], total protein, albumin) should be performed at each Day 1, Day 8, Day 15, and Day 22 visit.

Urinalysis by dipstick should be performed at baseline and at subsequent timepoints only if clinically indicated. Microscopic analysis must be performed by the hospital's local laboratory if required.

Bone marrow or blood cytogenetic samples may be collected from patients with prolonged hematological toxicities as defined under **Section 8.2.2.3** *Dose Modifications for Toxicities.* 

Additional analyses may be performed if clinically indicated.

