8.2.2.2 Olaparib Dose Modifications for concurrent Renal Impairment

If subsequent to study entry and while still on study therapy, a patient's estimated CrCl falls below the threshold for study inclusion ( $\geq$ 51 mL/min), retesting should be performed promptly.

For patients who develop moderate renal impairment (CrCl < 50 mL/min), hold dose until recovery.

Olaparib has not been studied in patients with severe renal impairment (creatinine clearance  $\leq$ 30 mL/min) or end-stage renal disease; if patients develop severe impairment or end stage disease, it is recommended that olaparib be discontinued.

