# 8.2.2.3 Olaparib Dose Modifications for Toxicities

Any toxicity observed during the course of the study could be managed by interruption of the dose of study treatment or dose reductions.

Patients who require an interruption in olaparib >4 weeks due to toxicity must discontinue all study therapy.

Olaparib can be dose reduced to 250mg twice daily as a first step and to 200mg twice daily as a second step with the exception of cases of CTCAE v5.0 grade 3 or 4 anemia when dose should be reduced to 200mg twice daily as first step. If the reduced dose of 200mg twice daily is not tolerable, no further dose reduction is allowed and all study treatment should be discontinued.

Once dose is reduced, escalation is not permitted.

For guidance on dose reductions for management of AEs (including renal impairment) refer to **Table 4 and Table 5**.

In case a dose reduction is necessary, the Study treatment will be administered as follows:

Table 4 Dose reductions for study treatment to manage adverse events

Initial Dose	Following re-challenge post interruption: Dose reduction 1	Dose reduction 2
300 mg twice daily	250 mg twice daily	200 mg twice daily

Table 5 Dose reduction for study treatment if patient develops moderate renal impairment

Initial Dose	Moderate renal impairment (calculated creatinine clearance by Cockcroft -Gault equation or based on a 24 hour urine test between 31 and 50 ml/min): Dose reduction
300 mg twice daily	200 mg twice daily

Table 6 Dose reductions for study treatment if patient has to start taking a strong or moderate CYP3A inhibitor

Initial Dose	Moderate CYP3A inhibitor	Strong CYP3A inhibitor		
300 mg twice daily	150 mg twice daily	100 mg twice daily		

For guidance on dose reductions when concomitant strong or moderate CYP3A inhibitors cannot be avoided refer to **Table 6**.

When dose reduction is necessary patients will take one 150 mg tablet and one 100 mg tablet twice daily or two x 100 mg tablet twice daily or one 150 mg tablet twice daily or one 100 mg tablet twice daily.

Management of hematological toxicity

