# **Renal Impairment**

If subsequent to study entry and while still on study therapy, a patient's estimated CrCl falls below the threshold for study inclusion ( $\geq$ 51 ml/min), retesting should be performed promptly.

A dose reduction is recommended for patients who develop moderate renal impairment (calculated creatinine clearance by Cockcroft-Gault equation or based on a 24 hour urine test of between 31 and 50 ml/min) for any reason during the course of the study: the dose of olaparib should be reduced to 200 mg twice daily.

Because the CrCl determination is only an estimate of renal function, in instances where the CrCl falls to between 31 and 50 mL/min, the investigator should use his or her discretion in determining whether a dose change or discontinuation of therapy is warranted.

Olaparib has not been studied in patients with severe renal impairment (creatinine clearance  $\leq 30$  ml/min) or end-stage renal disease; if patients develop severe impairment or end stage disease it is recommended that olaparib be discontinued.

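### The dosing sections rely on an entry floor of creatinine clearance 51 mL/min that the eligibility criteria do not contain, so a man with raised creatinine can start full-dose olaparib in the hold-or-reduce range

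*Combined protocol and SAP*

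**What the plan says.** **Eligibility.** Section 5.1 [11] sets a creatinine limit, "1.6 x ULN (for patients with" values at or above it having to show adequate clearance: "or measured creatinine clearance must be > 60" mL/min by Cockcroft-Gault. At lower creatinine no clearance is asked for. Section 5.2 has no renal exclusion, and 5.1 [7] sets no upper age limit.

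**Dosing.** Olaparib starts at 300 mg twice daily for everyone (Table 2, Section 7.6.1), with no renal starting dose. Section 8.2.2.2 asks for prompt retesting if "a patient's estimated CrCl falls below the threshold for study inclusion", and gives that threshold as at least 51 mL/min. It continues: "For patients who develop moderate renal impairment (CrCl < 50 mL/min), hold dose until recovery". The Renal Impairment text of 8.2.2.3 repeats the 51 mL/min threshold. For a clearance of 31–50 mL/min it recommends a reduction, "for any reason during the course of the study: the dose of olaparib should be reduced to 200 mg twice daily", but leaves the decision to the investigator's discretion. Table 5, headed "Dose reduction for study treatment if patient develops moderate renal impairment", gives the same 200 mg dose. At 30 mL/min or below, discontinuation is recommended.

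**Monitoring and screening.** The note in 7.3.1 on weekly monitoring covers "Patients with creatinine clearance between 51-100 mL/min either at trial enrolment or during the course of the trial", so its band also starts at 51. Section 7.2 has a general screening item: "Determine suitability for olaparib and ascorbate therapy".

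**The concern.** Three places (8.2.2.2, 8.2.2.3 and the 7.3.1 note) are written as if every man entered at 51 mL/min or more. Eligibility does not secure that. The hold in 8.2.2.2 and the reduction in Table 5 are worded for men who develop impairment on study, which presumes they began above the floor. The list of olaparib hold criteria in 8.1 has no creatinine or clearance item.

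Serum creatinine alone is a weak guide to clearance in this population, because the same creatinine means a lower clearance in an older or lighter man. A man who meets [11] as written could take a first dose of 300 mg twice daily at a clearance where the protocol's renal guidance points to 200 mg twice daily or no drug. He would also receive ascorbate, whose less common effects in 7.9.1 include nephropathy and renal failure. Section 4.2.8 says the combination has no clinical data in this disease. With 12 evaluable men planned, even one such case could make toxicity harder to attribute.

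**Working it through.** **Step 1: trace the cited threshold.** The 51 mL/min figure is a cross-reference, not a calculated quantity, so it has to be found in the eligibility criteria.

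| Place | Clearance figure | Applies to |
|---|---|---|
| 5.1 [11] | > 60 mL/min | only creatinine ≥ 1.6 x ULN |
| 5.2 | none | – |
| 7.3.1 note | 51–100 mL/min | at enrolment or on study |
| 8.2.2.2 and 8.2.2.3 | ≥ 51 mL/min | described as the inclusion threshold |

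It is in neither 5.1 nor 5.2.

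**Step 2: ask whether the creatinine limit does the same job.** The formula is the one [11] names, Cockcroft-Gault for men:

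clearance = (140 − age) x weight / (72 x creatinine in mg/dL).

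The multiples of ULN come from [11]. The laboratory ULN (1.2 or 1.3 mg/dL) and the grid of ages (65, 70, 75, 80) and weights (75, 80, 85, 90 kg) are assumptions; the documents give none of them. At these ULNs, [11] admits creatinine up to 1.6 x 1.2 = 1.92 or 1.6 x 1.3 = 2.08 mg/dL with no clearance check.

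Number of the 16 pairs below 51 mL/min, with the range of clearance over the grid:

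| Creatinine | ULN 1.2: pairs (range) | ULN 1.3: pairs (range) |
|---|---|---|
| 1.0 x ULN | 0 (52.1–78.1) | 1 (48.1–72.1) |
| 1.1 x ULN | 2 (47.3–71.0) | 6 (43.7–65.6) |
| 1.2 x ULN | 6 (43.4–65.1) | 10 (40.1–60.1) |
| 1.3 x ULN | 10 (40.1–60.1) | 13 (37.0–55.5) |
| 1.5 x ULN | 15 (34.7–52.1) | 16 (32.1–48.1) |
| 1.6 x ULN | 16 (32.6–48.8) | 16 (30.0–45.1) |

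**Step 3: examples.**

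- Affected: age 75, 80 kg. At 1.3 x 1.2 = 1.56 mg/dL, 65 x 80 / (72 x 1.56) = 46.3. At 1.5 x 1.3 = 1.95 mg/dL, 65 x 80 / (72 x 1.95) = 37.0.
- Affected outside the grid: age 60, 80 kg at 1.6 x 1.2 = 1.92 mg/dL, 80 x 80 / (72 x 1.92) = 46.3.
- Not affected: age 65, 90 kg at 1.3 x ULN, 55.5–60.1; age 70, 85 kg at 1.2 x ULN, 53.0–57.4.

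**Step 4: where clearance crosses 51.** The crossing multiple is (140 − age) x weight / (72 x 51 x ULN). The lower end is for ULN 1.3, the upper for ULN 1.2:

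- age 80, 75 kg: 0.94–1.02 x ULN
- age 75, 80 kg: 1.09–1.18 x ULN
- age 70, 85 kg: 1.25–1.35 x ULN
- age 65, 90 kg: 1.41–1.53 x ULN

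All four lie below the 1.6 x ULN that [11] allows.

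**The case against.** The best reply is that the gap is one of wording and that other provisions would catch the patient. The floor is stated twice in Section 8, and the 7.3.1 note cannot be applied at enrolment without estimating clearance. Chemistry is drawn at screening and weekly from cycle 1, and ascorbate starts only on day 8. A man who entered low could therefore be recognised within about a week, while on olaparib alone. The 8.2.2.3 text applies whatever the cause, 8.1 lets the investigator delay dosing for any laboratory abnormality, and 7.2 asks for a suitability judgement. At 31–50 mL/min that same 8.2.2.3 text recommends a reduction and allows discretion, so 300 mg is not flatly barred there, although 8.2.2.2 says to hold. Raised creatinine is the main driver: at 1.0 x ULN at most one of the 16 pairs falls below 51.

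Much of this stands as mitigation. It shortens the likely exposure, and it confines the problem largely to men with creatinine above the normal limit. It does not close the gap. None of these provisions makes clearance of 51 mL/min a condition of the first dose, and [11] is the rule on which sites will register patients. The retest and hold instructions speak of a fall or a development on study, which fits poorly a man who was already low at entry. The 7.3.1 note says nothing about a man below 51 at enrolment.

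**Conclusion.** The concern holds. The inclusion threshold cited in 8.2.2.2 and 8.2.2.3 does not exist in the eligibility criteria, and the creatinine limit in [11] is no substitute. Within the permitted creatinine range, between 0–1 of 16 grid pairs (at 1.0 x ULN) and all 16 (at 1.6 x ULN) fall below 51 mL/min. The absence of the threshold is a matter of reading and needs no assumption. The counts rest on Cockcroft-Gault, an assumed ULN of 1.2–1.3 mg/dL and the chosen ages and weights. They are not proportions of patients: the documents give no distribution of age, weight or creatinine, so the number affected among 12–15 men cannot be stated. This is a point of eligibility and dosing safety. It does not touch the primary endpoint, alpha, power or the decision rule.

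**What to change.** In 5.1 [11], keep the creatinine rule and add that every patient must have a Cockcroft-Gault or measured creatinine clearance of at least 51 mL/min, calculated from screening creatinine, age and weight. This is the figure the dosing sections already cite. In the same edit, make the second branch of [11] apply above 1.6 x ULN rather than at or above it, so that a value of exactly 1.6 x ULN falls under one rule only.

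The cost is one eligibility line. No new test is needed, since creatinine, age and weight are already collected at screening. Some men with low clearance and creatinine within 1.6 x ULN would fail screening. Their number cannot be estimated from the documents, and at the expected accrual of one patient per month each would matter a little.

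The edit does not settle a separate conflict for men whose clearance falls on study: 8.2.2.2 holds olaparib below 50 mL/min, while Table 5 and the Renal Impairment text reduce it to 200 mg twice daily at 31–50. The sponsor should choose one rule when making this change.
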